8.1 Study design

The design is a pragmatic randomized controlled trial (24, 25).

8.2 Time plan

A summary of the time plan for participants' visits in the study as well as for interviews and acquisition of register data from the National Board of Health and Welfare is shown in the figure below.

8.3 Setting and research environment

VIPVIZA is integrated in the Västerbotten Intervention Program (VIP) (26), which is a population-based CVD screening and prevention program in the County of Västerbotten, Sweden (population 265,000). Since the 1990s, VIP has provided health surveys for all county inhabitants during the year in which they turn 40, 50 and 60 years (n=6500-7000/year), comprising CVD risk factor screening and individual promotion of healthy lifestyle and pharmacological CVD prevention.

To date, over 170,000 health surveys have been performed. Participation rates during recent years were around 60-70% with only small social selection bias (27). VIP is one of the largest long-term CVD prevention programs in the world. It provides a unique arena for pragmatic studies of population-based CVD risk intervention

The ultrasound examinations in VIPVIZA are performed at the hospitals in three cities/towns (Umeå, Skellefteå, Lycksele), and in remote rural areas at primary health care centres. Risk factor measurements and questionnaires at follow-up are carried out for participants in Umeå at the Clinical Research Centre at Umeå University Hospital, and for participants in the rest of the county at their local primary health care center.

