Medical Biobank, Umeå University Hospital. Written information about ultrasound results are sent to all SPs and their respective family physicians in primary care.

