- At the 3-year follow-up: Invitations and appointment time for the ultrasound examination, risk factor measurement and questionnaire completion is sent by post to participants living in Umeå and surrounding municipalities by research nurses at KFC; all examinations are conducted at KFC. Participants outside this area are also invited for ultrasound examinations undertaken in hospitals in the three towns in Västerbotten County (Umeå, Skellefteå and Lycksele), and at the local primary health care centres in rural areas. Invitations are sent only once, with no reminder following non-attendance. . Research nurses also inform the health care centers outside the Umeå area when it is time to invite participants to the 3-year visit, although this visit is managed by the health care centers, including risk factor measurements and questionnaire completion. At this time point, the intervention group also answer questions about how they perceived the pictorial information and phone call received at baseline concerning the ultrasound results.

Results of clinical risk factor measurements and the completed questionnaires are sent to KFC and the research nurses give feedback to participants using a predefined form similar to the form used at the 1-year follow-up.

Within two weeks of the carotid ultrasound examination, information about the results are sent by post to the participant, see 12.2.2. At the same time, exactly the same information is sent to their respective primary care physician. After an additional 2-6 weeks, participants whose ultrasound results indicated CIMT values higher than expected according to age and sex (red gauge) or with plaques (red), receive a follow-up phone call by a research nurse in order to ascertain whether the information is accurately understood and to reassure the participant and give additional information if needed. Participants without plaques (green) or vascular age similar or lower than expected (green or yellow/orange gauge) are informed by a standard letter including the contact information for research nurses, in case of questions or concerns.

Qualitative interviews are conducted with a few SPs, regarding their experience of receiving the second ultrasound report and how they interpreted this in relation to any life style modification carried out, including taking prescribed medications, following the first ultrasound examination.

[figure not shown]

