## **Amendment 2 to the Statistical Analyses Plan**

**Evaluation after 6 years**

**CVD risk scores, CVD risk factors, and ultrasound data**

**2024-01-12**

## **VIPVIZA Amendment 2 to the Statistical Analyses Plan**

The present amendment to the VIPVIZA statistical analysis plan includes details on planned analyses of the VIPVIZA intervention after 6-year follow-up, to be presented in two publications: one evaluating the CVD risk (study A) and one evaluating cIMT and atherosclerotic plaque progression (study B). For the analysis of the 6-year follow-up of VIPVIZA, the description of outcome variables and study populations of the original VIPVIZA statistical plan is still valid, unless otherwise noted in this amendment.

The 3-year follow-up examinations were performed from September 5 2016 to May 28 2019 and all participants from both groups, as well as their respective family physicians in primary care, received the pictorial and written result of the ultrasound examination. Thus, directly after the VIPVIZA 3-year follow-up, all participants in the initial control group (IC) underwent the intervention for the first time and the initial intervention group (II) underwent a second (repeated) intervention. This means that the arms of the trials are no longer parallel and that studies following the progression of the groups after the 3-year follow-up will be post-trial evaluations that no longer allow for estimation of the VIPVIZA intervention effect through direct comparisons of IC and II. Even so, it is still of interest to evaluate the long-term development of the two arms, and to investigate if there still exist group differences in CVD risk and severity of atherosclerosis, e.g. due to the different lag times from when the intervention was given. Furthermore, there are few studies about the development over time of riskfactors and atherosclerosis (assessed by imaging, ultrasonography). Therefore, we will investigate development (regression-progression) of risk factors for CVD and atherosclerosis as assessed by carotid ultrasonography in the complete study population and subdivided in combinations of subgroups, and in particular on age groups (40-, 50- and 60 year old), sex, educational level, severity of ultrasound result. We will also separately analyze scenarios with worst vs best development (e.g. groups of individuals with severe progression vs groups with regression).

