Prevalence ratio of smoking will be estimated from Poisson regression with robust Huber-White sandwich estimator of standard errors, adjusting for baseline smoking status. All ANCOVA/Poisson models will be fitted with and without adjustments for sex and educational level.

For SCORE2, group differences at 1-years and 3 years will be estimated using previously described ANCOVA model.

In addition, we will conduct stratified analyses by:

- Sex/Gender (men/women)
- Age-groups at baseline (40, 50 or 60 years).
- Baseline educational level
- Risk level at baseline
- Severity of ultrasound result

The main analysis will be performed on complete case data. Analyses using multiple imputation of missing data will be performed as secondary analyses. No correction for multiple comparisons to control the familywise error rate will be performed. This is motivated

by the fact that this is a post evaluation of the original trial and does not fall under the convention of adjusting for multiplicity within randomized trials.

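### Outside the Umeå area nothing readable requires the 3-year risk-factor visit to precede the posted scan result, so some controls could have been measured after disclosure; a date-based sensitivity analysis would settle it

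*Protocol*

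**What the plan says.** **Where and by whom the 3-year visit is done.** For Umeå and surrounding municipalities, protocol 12.2.1 states that "all examinations are conducted at KFC". For everyone else there are two streams. The scan: "Participants outside this area are also invited for ultrasound examinations undertaken in hospitals in the three towns in Västerbotten County", or at local centres in rural areas. The rest of the visit is left to the health centres: research nurses tell them when an invitation is due, "although this visit is managed by the health care centers, including risk factor measurements and questionnaire completion". Section 8.3 agrees that follow-up measurements are made in Umeå at the research centre "and for participants in the rest of the county at their local primary health care center".

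**When results are disclosed.** Protocol 12.2.1: "Within two weeks of the carotid ultrasound examination, information about the results are sent by post to the participant", with the same report going to the primary care physician. Protocol 9.2.4: "Written information about ultrasound results are sent to all SPs and their respective family physicians in primary care". Section 12.3 gives controls the same 3-year procedures, apart from the questions on the baseline report and phone call and the qualitative interviews.

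**What the SAP assumes.** The introduction to SAP Amendment 2 says that "directly after the VIPVIZA 3-year follow-up, all participants in the initial control group (IC) underwent the intervention for the first time", and that later comparisons of the arms are post-trial evaluations. Study A nevertheless returns to the 3-year contrast: "For SCORE2, group differences at 1-years and 3 years will be estimated using previously described ANCOVA model".

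**The concern.** The posted ultrasound report is the intervention. A control who has opened the letter, or whose physician has the report, is no longer an untreated control. The posting clock starts at the scan and does not wait for the health-centre visit. Outside the Umeå area, following the procedures as written can therefore put disclosure before the 3-year blood pressure, lipids, lifestyle, self-rated risk, self-efficacy and psychometric questionnaires.

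Year 3 is the last time point at which the arms differ as randomised. It is named in the Objective (protocol 6.1), and Study A will use it for a new SCORE2 estimate and in its repeated-measures model. If controls have begun to respond, the difference between arms shrinks. Self-rated risk, self-efficacy and anxiety could move as soon as the letter is read; lipids and blood pressure would need longer. Because the separate visits exist only outside the Umeå area, any dilution could also look like a geographic difference in effect.

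**Working it through.** **Step 1. Is there an ordering rule?**

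| Place | What it settles |
|---|---|
| Protocol 9.2.4 | Lists risk factors and questionnaires, then the scan, then written results; sets no order or gap |
| Protocol 9.3, activity scheme | Shows a single 3-year visit; 12.2.1 describes two streams outside the Umeå area |
| Protocol 12.2.1 | Letter timed from the scan only; not held for the other visit |
| Protocol 12.3 | Same timing for controls |
| Protocol 13.2.3 | Methods at 3 years similar to those at 1 year; visit order not addressed |
| SAP Amendment 2, introduction | Describes disclosure as following the 3-year follow-up; gives no date rule |

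Measurement before disclosure is implied in places but required nowhere in the readable text.

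**Step 2. Which outcomes are exposed?** The primary comparison is at 1 year (protocol 13.2.3), before any control disclosure. CIMT and plaque at 3 years are recorded at the scan itself, so that scan's letter cannot alter them. What remains is 3-year risk scores, risk factors and questionnaires outside the Umeå area.

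**Step 3. Reproduce the plan's figures.** Protocol 13.1 uses alpha 0.05, power 0.80 and 1500 per group. With z-values 1.960 + 0.842 = 2.802 and sqrt(2/1500) = 0.03651:

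- SCORE: 1.40 × 2.802 × 0.03651 = 0.143 (stated 0.143)
- SBP: 16 × 2.802 × 0.03651 = 1.64 (stated 1.7)
- Framingham: 6.60 × 2.802 × 0.03651 = 0.675 (stated 0.7)

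The table reproduces to rounding for these rows.

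**Step 4. Dilution, under assumptions.** Let f be the share of controls measured after disclosure and r the share of the full effect they have already realised. If only controls respond, the fraction of the effect kept is 1 − f × r. The documents give neither f nor r. Assumed values:

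- f = 0.10, r = 0.10: 1 − 0.01 = 0.99
- f = 0.25, r = 0.25: 1 − 0.0625 = 0.9375
- f = 0.20, r = 1 (full response): 0.80
- f = 0.50, r = 0.50: 1 − 0.25 = 0.75

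Power = Φ(kept × difference / (SD × 0.03651) − 1.960), at 1500 per group:

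| Difference | Undiluted | 0.99 kept | 0.9375 kept | 0.80 kept | 0.75 kept |
|---|---|---|---|---|---|
| SBP 2 mmHg | 0.928 | 0.924 | 0.894 | 0.78 | 0.728 |
| Framingham 1 point | 0.986 | 0.984 | 0.973 | 0.91 | 0.875 |
| SCORE 0.5 | 1.000 | 1.000 | 1.000 | 1.00 | 1.000 |
| SCORE 0.143 | 0.799 | 0.791 | 0.746 | 0.61 | 0.555 |

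The first three rows use the protocol's own relevant changes; the last uses its minimum detectable SCORE change. No SD for SCORE2 is given, so SCORE stands in for it. The ANCOVA planned in Study A adjusts for baseline and would not have exactly these powers.

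**Step 5. Direction.** The intervention arm gets a second letter on the same timetable. If its late-measured members gain a further fraction g of the effect, and f is equal in both arms by randomisation, the fraction kept is 1 − f × (r − g). A first disclosure plausibly moves people more than a repeat (g < r), which gives dilution. If g = r there is no net bias, and if g > r the contrast would be exaggerated.

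**The case against.** **The contrast cannot be said to be diluted.** A reader might infer from the procedures that controls were in fact measured after disclosure. The documents do not show this. They give no visit order, no gap, no share of participants outside the Umeå area and no speed of response. The running order in 9.2.4, the single 3-year visit in 9.3 and the SAP's account all lean towards measurement first. In rural areas the scan may take place at the same health centre. The 6-year dates in the SAP show risk-factor collection starting on December 1 2019 and scans on January 13 2020, so the two streams can run apart, but this says nothing about order at 3 years. This objection stands, and limits the point to a possibility.

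**Part of the material is not visible.** The time plan (8.2) and flow chart (9.1) are figures that cannot be read here, and the original analysis plan was not available. An ordering rule could be there. This stands as a caveat; the readable text has none.

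**Severe power loss is not shown.** A reader might start from 80% power, assume full response and reach 71%, 61% or 50% at 10%, 20% or 30% contamination. That arithmetic is right, but it assumes complete response by the visit and an effect no larger than the minimum detectable one. The row that set the sample size is CIMT, which is not exposed. At the protocol's own relevant changes, 20% full contamination still leaves 0.78 for SBP, 0.91 for Framingham and 1.00 for SCORE.

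**It is late.** The 3-year examinations ended in May 2019, and the SAP reports that 1-year and 3-year differences have been published for the other Study A outcomes. A scheduling rule would change nothing now. This stands for the protocol, but not for the SCORE2 contrast that the SAP, dated January 2024, still plans.

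**Conclusion.** The gap is real, but its consequence is unknown. Outside Umeå and surrounding municipalities the visit rules do not secure the SAP's statement that controls were informed only after their 3-year follow-up. The 3-year contrasts for risk scores, risk factors and questionnaires can be diluted, most likely towards zero. That direction rests on controls responding more to a first letter than the intervention arm does to a second.

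The size cannot be computed from the documents. Across the partial-response scenarios, 1% to 25% of the effect would be lost. Power for a SCORE difference of 0.5 is untouched, and power for a difference of 0.143 falls from 0.80 to between 0.79 and 0.56. These figures illustrate; they do not estimate.

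A reader might go further and take this as casting doubt on the trial's main result or its imaging findings. The documents do not support that, since neither the 1-year primary outcomes nor 3-year CIMT and plaque can be affected by the 3-year letter. This is a cheap improvement to one remaining planned contrast, and to any other 3-year risk-factor or questionnaire contrast that is reported.

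**What to change.** Add to SAP Amendment 2, Study A, wording such as:

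> In both arms, participants whose 3-year risk-factor or questionnaire date is later than the posting date of their 3-year result letter will be flagged, and their number reported by arm. If posting dates were not recorded, the scan date will be used instead. The 3-year SCORE2 difference, and any other 3-year risk-factor or questionnaire contrast reported, will be repeated without the flagged measurements as a sensitivity analysis.

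Using the scan date is conservative: it also flags people measured between the scan and the letter. Applying the same rule in both arms addresses the intervention arm's second letter. A count near zero would confirm the SAP's description; otherwise readers need the number.

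**Cost.** One count and one repeat analysis. Protocol 14.2 says the CRF holds administrative information on visits, but does not mention posting dates, so the scan-date version may be the feasible one. The sensitivity set is smaller and is selected on a date that arises after randomisation, so it supplements the main analysis and does not replace it.

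A protocol rule that 3-year measurements be completed before the result letter is posted would have been the design remedy. It can no longer alter the completed 3-year visits.

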8.4 Risk-benefit evaluation for the individual

The intervention in VIPVIZA is the provision of pictorial information about the presence and extent of the individual's atherosclerosis from their ultrasound results. This is considered to be a low-intensity intervention in comparison to interventions with pharmacological drugs or surgical procedures. The ultrasound examination cannot cause any harm, physical discomfort or risk.

As with all screening which targets a healthy population, it is a dilemma whether or not to inform asymptomatic individuals of silent disease, in this case an ongoing atherosclerotic process with increased risk of future CVD. The presence of atherosclerosis can be perceived by the subject as more serious than just an increased level of risk markers, and may therefore result in anxiety. In order to avoid unjustified concerns, all persons in the intervention group receive a telephone call from a research nurse and, if necessary, a doctor in charge, to give in-depth and balanced information about the ultrasound results. This conversation is conducted according to the methodology of motivational interviewing and also aims to increase awareness of the possibility of reducing the individual's risk by means of their own preventive measures. This is expected to alleviate anxiety and increase motivation to follow the recommendations for preventive treatment. According to the study hypotheses, this is expected to benefit the individual due to risk reduction and a more healthy lifestyle is also expected to bring benefits through increased well-being and quality of life. Similarly, subjects without ongoing atherosclerotic disease will be able to avoid unjustified concerns that their risk factors, if any, may be contributing to an active disease process.

All individuals with severe carotid stenosis will be excluded from the study and are referred directly to the Stroke Center for assessment and treatment. This may potentially be life-saving for these people, and may, to some extent, mitigate the fact that no information is provided to half the group until 3 years after they enter the study, even if small/moderate changes are detected.

8.5 Discontinuation of the study

[figure not shown]
Individuals at high risk of stroke, defined as severe carotid stenosis, i.e. stenosis >50% of the lumen, are excluded from the study, informed of the results and referred to the Stroke Center, University Hospital, Umeå, with treatment in accordance with current guidelines for this group.

8.6 Pilot study

A pilot study with 95 participants was performed September-October 2012. The study organisation worked well and protocols and procedures were further developed and showed good feasibility, although randomization to intervention and control groups was not carried out. In order to optimize understanding of atherosclerosis as a process and the accurate perception of the ultrasound result, the information was calibrated according to participants' experiences and suggestions, collected through questionnaires and interviews. After 3 years, complete data on risk factors from 81 pilot participants was collected, and favorable changes regarding LDL-cholesterol, triglycerides and fasting glucose were observed, with the addition of favorable weight changes among women only.

[figure not shown]
9. Study plan, the main study

9.1 Flow chart

9.2 Visits

9.2.1 Baseline visit, participation in VIP. Data collection: demographic, socio-economic, clinical risk factors for CVD, and lifestyle. This data is used in an individual health dialogue with a trained district nurse at the primary health care center. Applying the methodology of Motivational Interviewing, this session aims at health promotion and CVD prevention. A pictorial tool, the “Star profile” (Figure below), is used to facilitate the individual’s understanding of how his/her lifestyle is linked to CVD risk factors.

When requested, VIP-participants are also recommended follow-up visits or referrals to the family physician for pharmacological treatment according to guidelines. Samples of blood are frozen and stored at the Biobank, Umeå University Hospital.

VIP participants who are eligible for participation in VIPVIZA are given written and verbal information about the VIPVIZA study and are invited to the study at the occasion of their participation in VIP at their primary health care centre. The district nurses who conduct the health dialogues also sign that the study information is given and collect the informed consent forms and send them to research nurses at KFC. The research nurses register all forms. Appendix 1: The Informed Consent form translated from Swedish to English

9.2.2 Baseline visit with ultrasound examination. Study participants are randomized into two equal groups, intervention and control, following a computer-generated randomization list. They then complete psychometric questionnaires, questions about self-rated risk of CVD and health-specific self-efficacy, and undergo the first ultrasound examination of both carotids. Written information about results are sent to those in the intervention group and their respective family physician in primary care.

9.2.3 Follow-up one year after the ultrasound examination. Measurement of clinical risk factors for CVD, lifestyle, self-reported pharmacological treatment, self-rated health, risk of CVD and health-specific self-efficacy. Framingham Risk Score and Score are estimated.

9.2.4 Follow-up three years after the ultrasound examination Data collection: clinical risk factors for CVD, completion of lifestyle questionnaire, psychometric questionnaires, questions about self-rated risk of CVD and health-specific self-efficacy. Participants also undergo the second ultrasound examination of both carotids. Samples of blood are drawn, frozen and stored at the

Medical Biobank, Umeå University Hospital. Written information about ultrasound results are sent to all SPs and their respective family physicians in primary care.

